### 2. Objectives

#### a. Purpose

Measurement Based Care (MBC) is the systematic, routine evaluation of symptoms to inform care decisions. Especially in youth, MBC increases the rate of symptom improvement, detects clients who would otherwise deteriorate, and alerts therapists to non-responders. Despite its demonstrated utility, MBC is rarely implemented with fidelity; fewer than 15% of therapists report using MBC per recommendations. Previous efforts to support MBC implementation have yielded suboptimal outcomes because Community Mental Health Clinic (CMHC) leaders are challenged to identify and prioritize barriers and select strategies to overcome them. New methods are needed to optimize MBC implementation and treatment quality to improve youth mental health outcomes in community settings. The purpose of this project (referred to as NIMBLE) is to pilot test and refine IMPACT Center methods in six diverse CMHC clinics across Washington state (three of six serve primarily Latinx populations) to optimize MBC implementation.

#### b. Primary Objective/Aim

##### **Aim 1: Co-create plans for optimizing Measurement Based Care (MBC) implementation for youth with comorbidities.**

We will test IMPACT methods to identify and prioritize barriers of MBC implementation, and to select and match strategies to prioritized barriers. IMPACT methods include (a) **rapid evidence reviews** to uncover empirical data regarding MBC barriers (therapists only); (b) **rapid ethnography** to identify and describe local barriers and situate them in specific organizational, social, and task contexts (therapists & clinic staff only); and (c) **design kits** (e.g., kits with disposable camera, journals) to allow *therapists and youth* to capture and reflect on aspects of their context that are salient for MBC. These three methods will result in a list of barriers that will be rated by therapists and other staff who agree to join a clinic specific implementation team. Subsequently, we will use facilitated group processes (**barrier prioritization and causal pathway diagramming**) to develop plans to match strategies to the top three barriers and clarify what needs to be in place to optimize

MBC implementation. We will check back with clinic-specific implementation teams biweekly to track strategy deployment for six months; after 3 months if MBC hasn't significantly improved, clinic teams will move onto deploying their other strategies.

### **c. Secondary Objectives/Aims**

#### **AIM 2: Compare MBC fidelity post IMPACT Center methods deployment versus historical controls.**

We will evaluate at the clinic level whether IMPACT methods were effective in optimizing MBC fidelity. To do this, we will employ two methods: 1) an **anonymous self-report survey** pre-implementation, 3 months and again 6 months post implementation strategies, and 2) a historical control design comparing MBC fidelity pre- and post- IMPACT methods (e.g., design kits). **Pre-IMPACT method** data will be captured from a pre-existing, routinely gathered, de-identified database from the Washington State CBT+ initiative (**further described in Section 6 – Setting**). The database will represent MBC fidelity 2 years prior to IMPACT center methods. For **post-IMPACT method** data, at least 5 therapists at each clinic will be asked to report MBC fidelity data to the Washington State CBT+ Initiative Dashboard for up to 5 cases. Therapists at each clinic are familiar with the Dashboard, as its use is part of their routine training. Data recorded related to MBC fidelity consists of therapist's use of the three main components of MBC – (1) Collect, (2) Share, and (3) Act (described further in **Scientific Background** and **Study Procedure** sections).

### **3. Background Information and Rationale**

#### **a. Scientific Background**

MBC is effective in improving mental health outcomes for youth with comorbidities but only if implemented with fidelity. MBC is the systematic evaluation of youth outcomes (like symptoms) before or during each clinical encounter to inform care. When relying *only* on clinical judgement, therapists detect few cases of client deterioration (only 21.4%). When implemented with fidelity, MBC consistently yields medium effect-sized improvements over usual care and can be especially beneficial for guiding treatment focus with youth who have comorbidities. For youth in community mental health clinics, where comorbidities are the rule rather than exception, MBC holds powerful promise for increasing the quality of any psychological intervention by facilitating communication and focusing treatment.

We operationalize MBC's fidelity elements in accordance with Barber & Resnick's transtheoretical model called Collect, Share, Act. Collect refers to the routine administration of symptom measures before therapy sessions. Share refers to therapist and client score review. Act refers to collaborative reevaluation of the treatment plan. Each element is necessary to maximizing the promise and clinical utility of MBC.

Bickman and colleagues studied MBC implementation at two clinics. Higher implementation with fidelity corresponded to better youth outcomes at one clinic, despite facing more discrete barriers. The clinic with poor outcomes did not address key barriers

(e.g., leadership buy-in), suggesting that lack of barrier prioritization undermined MBC fidelity. Similarly, Lewis found that clinic-led tailoring improved one of three elements of MBC fidelity (measure administration). However, score review and reevaluation of the treatment plan remained suboptimal. Without rigorous methods to support the practice community in optimizing all MBC elements, or treatment quality will remain low, and youth will not experience mental health benefits.

**This study is the first signature project of the IMPACT center in partnership with the Washington State CBT+ initiative.** The current project uses new methods, including rapid evidence synthesis, rapid ethnography, and design kits to identify locally contextualized barriers to clinic-wide use of MBC, as well as causal pathway diagramming (CPD) a method for selecting strategies and matching them to barriers that will help clinics optimize their use of MBC (Aim 1.) We will investigate whether IMPACT methods improve MBC fidelity through a historical control design (Aim 2).

[figure not shown]
**b. Preliminary Data**

None.

#### **4. Study Design**

The study design is a prospective implementation study that includes a retrospective database review arm. We will pilot IMPACT's methods in six clinics in partnership with the CBT+ initiative. We will approach clinics that are diverse in patient makeup (e.g., approaching clinics that see primarily Latinx youth), rural/urban status, size, and length of time implementing EBPs. There will be 2 cohorts of 2 clinics each, staggered by 6 months. Total duration of the study for participating clinics is 24 months.

The study design is represented in picture form in Figure 1 below. Figure 1 is broken down by aim and site visit. In the diagram, Aim 1, activity 1 is coded as A1a, Aim 1, activity 2 is coded as A1b, and

so forth.

**Figure 1 – Map of the NIMBLE study**

Note on in-person/hybrid/virtual study activities: All study activities may be done in-person or virtually, depending on clinic preference and staff availability. For any virtual activity, we will use the KP Microsoft Teams platform or the clinic's preferred HIPAA-compliant teleconferencing platform.

### **Aim 1 (A1): Co-create Plans for Optimizing MBC Implementation for Youth with Comorbidities**

To identify barriers to using MBC with fidelity, IMPACT will pilot 3 new, complementary methods: rapid evidence reviews (RER), rapid ethnographic assessment (REA), and design kits and further pilot causal pathway diagramming.

#### **A1a: MBC training (Site visit 1)**

**The title of the training is:** Collect, Share, Act – making measurement-based care work for your youth mental health practice.

**Description of the training:** Measurement-based care (MBC) is a promising addition to any psychological treatment for any mental health problem. This one-time training offers an

overview of MBC: what it is, why it works, the primary components, typical challenges, and strategies for use with minoritized youth with complex psychosocial presentations.

**A1b: Build engagement and identify context-specific barriers through rapid ethnographic assessment (Site visit 1)**

Understanding implementation context is critical to the success of implementation efforts, as it allows you to better match strategies to barriers. Several methods exist to understand the implementation context, but their use brings up a myriad of conceptual and philosophical difficulties. In this study, we use REA methods over 2-day virtual or in-person site visits at each clinic.

**A1c: Identify barriers using design kits (Site visit 1)**

To complement REA and collect real-time data from therapists and youth, at the end of site visits, we will leave (or mail out) design probe materials including disposable cameras, journals, pens and prompts to use to take pictures, make diary entries, draw maps, and record images.

**A1d: Barrier prioritization (Site visit 2)**

To prioritize barriers to using MBC with fidelity, IMPACT will pilot a new group-facilitated activity with our clinic staff participants. The activity will occur in-person (Site Visit 2) but could be delivered virtually if needed. Identified barriers (50+ expected) will be prioritized using a participant-engaged method. We will engage 5-8 therapists and/or staff in the prioritization activity for a 2-hour facilitated group activity.

**A1e: Co-generate implementation plans/Causal Pathway Diagramming (Site visit 3)**

Following the prioritization of barriers, causal pathways diagrams (CPDs) will be used to compare and select implementation strategies best suited to address the barriers of using MBC with fidelity. The same implementation team members will be engaged in this 2-hour in-person or virtual activity as in Site Visit 2.

**A1f: Focus groups to improve IMPACT methods (Site visit 4)**

We will engage our partners in a semi-structured focus group to capture their experience engaging in all IMPACT Center methods in the 3 site visits to inform further toolkit refinement. This will occur in person or virtually.

**Aim 2 (A2): Compare MBC fidelity post IMPACT Center methods deployment versus historical controls (no site visit)**

The purpose of IMPACT methods is to improve clinician's fidelity using MBC. Fidelity will be conceptualized as therapist's use of the three main components of MBC – (1) Collect, (2) Share, and (3) Act. We will assess fidelity in two ways. First, we will use a brief anonymous self-report survey before implementing strategies and 6 months after. Previously, we had planned to use data from the Washington State CBT+ Initiative Dashboard, but we have had difficulty recruiting clinicians to engage in this task. For our second method of fidelity measurement we will ask clinics to send a dataset from their electronic health record for at least 6 months before IMPACT methods were deployed, and to 6-months after the active implementation period. The dataset will not contain any PHI. We will compare historical data at 6- and -18 months post site visits. .

## 5. Study Population

### a. Number of Subjects/Participants

Aim 1: Co-create plans for optimizing Measurement Based Care (MBC) implementation for youth with comorbidities.

#### Therapists/Clinic Staff:

Rapid Ethnographic Assessment Interviews – 120 participants

Design Kit – 32 participants (subset of the 120 interviewed)

Barrier Prioritization – 24 participants (subset of 120 interviewed)

Causal Pathway Diagramming – 20 participants (subset of 120 interviewed)

Focus Groups to improve IMPACT methods– 20 participants (subset of 120 interviewed)

#### Youth:

Design Kit - 32 participants

### AIM 2: Compare MBC fidelity post IMPACT Center methods deployment versus historical controls (not associated with a site visit)

NIMBLE will compare data at a clinic level prior to MBC training and at 6- and 18-months post site visit 1.

Our approach is to evaluate, at a clinic level, use of MBC before and after IMPACT method deployment. Specifically, we focus on whether therapists engaged in the main components of MBC: (1) Collect, or how often measures were provided to patients (frequency of administration), (2) Share, or how often therapists discuss outcome measures with their patients, and (3) Act, or whether therapists and patients used outcome measure data to change their direction in therapy (reevaluation using data).

We will use two different methods to assess use of MBC. The first is a short anonymous self-report survey filled out before implementing new strategies to address barriers to MBC use, and a second time 6 months after implementation. The second method is to ask for 5 therapists to enter data from 5 cases related to MBC use into the Washington State CBT+ Dashboard. Data will be aggregated at the clinic level, as we are investigating whether IMPACT methods impact clinic-wide changes. We are not studying whether any individual person's behavior changes as a result of IMPACT methods.

Clinic staff/Therapists (N=30) across 4 CMHCs in Washington state.

Inclusion: Must be aged 21+ and be working at a CMHC that is participating in the WA State CBT (Cognitive Behavioral Therapy) + Initiative.

Exclusion: Must be willing to participate in study activities

Youth participants: NA, there are no Youth Participants in this aim

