**A1f. Focus Groups to Improve IMPACT methods.** We will engage our partners in a semi-structured focus group to capture their experience engaging in all IMPACT Center methods in the 3 site visits to inform further toolkit refinement. A facilitator not previously engaged in any of the activities will conduct a 90-minute focus group to solicit reactions to all aspects of IMPACT's methods, including the steps and personnel requirements of each method, and their output (e.g., prioritized barriers; utility of the information captured in the CPDs). We will also be collecting implementation outcome measures, Acceptability, appropriateness, feasibility using established measures. The focus group data will supplement observer notes taken throughout the site visits.

To gather quantitative data related to IMPACT methods, up to N = 30 workshop participants will also be asked to complete Weiner et al.'s (2017) acceptability of intervention measure (AIM), feasibility of intervention measure; (FIM), and intervention appropriateness measure (IAM). The focus of these measures will be on assessing the acceptability, feasibility, and appropriateness of IMPACT center methods (e.g., design kits). These measures are uploaded in the IRBNet submission.

**AIM 2 (A2): Compare MBC fidelity post IMPACT Center methods deployment versus historical controls.** To examine MBC fidelity in Aim 2, we use routine session process data entered by therapists as part of their participation in the Washington CBT+ Initiative. In addition, we will request that therapists fill out a short anonymous self-reported survey on outcome use before the active implementation period, at 3 months and again at 6 months (REDCap survey: MBC Outcome Questionnaire).

[name] is a co-director of the Washington State CBT+ Initiative and the MPI of the IMPACT center. The dashboard with de-identified cases from which we are collecting data from is maintained as part of the CBT+ Initiative, and the CBT+ Initiative is the primary "laboratory" for IMPACT center methods. When data from CBT+ aligns with IMPACT aims, data can be curated by their team and sent to IMPACT NIMBLE co-investigator [name], via secure file transfer per CBT+ operational guidelines and procedures. Data will be shared back with clinics and the CBT+ initiative only in aggregate form for the purposes of quality/continuous improvement. CBT+ has routinely used data from the dashboard for quality improvement over the past 10 years.

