#### **b. Storage of data and/or specimens.**

All data will be stored on password-protected computers on the study G-drive accessible only to IMPACT Center Study Staff or on the KPWA REDCap platform. Physical documents will be stored at MPE in locked filing cabinets only accessible to study staff. All materials will be de-identified, using a unique study ID that does not require a crosswalk because we only need to know which

documents correspond with each other. Because this is de-identified data, it will be kept indefinitely. Postage paid self-addressed sealed envelopes will be sent back by USPS. All audio and digital recordings of rapid ethnography interviews will be kept on the G-drive or Sharepoint site with access only granted to research staff on the IRB.

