UPDATES: We deviated from the original analytic plan because we were unable to recruit clinicians to track outcome data using the CBT+ toolkit. Instead, and as documented in the protocol, we sent providers a Qualtrics form asking them to self-report their caseload as well as the number of clients they reported using measurement-based care with. The updated analytic plan based upon this change is as follows: Descriptive statistics will be used to summarize fidelity to measurement-based care (MBC) at each of the three assessment time points. A repeated-measures analysis of variance (ANOVA) will be conducted to evaluate whether fidelity to key components of MBC changes over time—from baseline (defined as 6 months post-enrollment) to 3 months after the conclusion of active implementation, and again at 6 months post-implementation. No statistical corrections for multiple comparisons will be applied given the single statistical test being carried out. Statistical significance will be evaluated at the 0.05 level (two-tailed). To address missing data, a conservative **Last Observation Carried Forward (LOCF)** approach will be used, allowing participants with partial data to be retained in the analytic sample. Assumptions of normality and sphericity will be assessed. If the assumption of sphericity is violated, Greenhouse-Geisser corrections will be applied. Effect sizes (e.g., partial eta squared) will be reported to estimate the magnitude of observed effects. All analyses will be conducted using R v4.3.3 and Rstudio 2023.12.1].

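### The SAP's only test needs each respondent's survey waves to be linked, but the protocol calls the survey anonymous and neither document says how waves are matched

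*Protocol*

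**What the plan says.** The protocol calls the self-report survey anonymous in four places, all under Aim 2:

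- Section 2c, which sets the waves at "pre-implementation, 3 months and again 6 months post implementation strategies".
- Section 4: "we will use a brief anonymous self-report survey before implementing strategies and 6 months after".
- Section 5a: "The first is a short anonymous self-report survey filled out before implementing new strategies to address barriers to MBC use".
- Section 8a: "we will request that therapists fill out a short anonymous self-reported survey on outcome use before the active implementation period".

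Section 5a also says that data will be aggregated by clinic, and adds: "We are not studying whether any individual person's behavior changes as a result of IMPACT methods".

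The SAP, under UPDATES, reports that therapists could not be recruited to track cases in the dashboard. A Qualtrics self-report form therefore supplies the fidelity data. For the three time points, "A repeated-measures analysis of variance (ANOVA) will be conducted". Missing waves are filled by LOCF, "allowing participants with partial data to be retained in the analytic sample". The SAP describes this as a single statistical test, at the two-sided 0.05 level.

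**The concern.** In the SAP's analysis the rows are participants and the repeated factor is time. A repeated-measures ANOVA removes stable differences between respondents from the error term, so it must know which baseline response belongs to which later response. LOCF needs the same information, because it has to identify who is missing at a later wave and which earlier value is theirs. A survey that is anonymous in the ordinary sense supplies neither.

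The two documents also differ on the question being asked. The protocol asks about change in a clinic and sets aside change in a person. The SAP's method is built on change in a person.

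This ANOVA is the only inferential test left in the updated plan. If the responses are unlinked, the analyst must pair rows arbitrarily, ignore the within-person structure, or choose another method after seeing the data.

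**Working it through.** **1. Is there a link anywhere in the documents?** These are the places where one might be found.

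- Protocol 9b gives stored materials a "unique study ID that does not require a crosswalk", so that documents belonging together can be matched. It does not name the survey or say that respondents enter an ID at each wave.
- Protocol 9a lists the data protected by study ID: interviews, design kits, barrier prioritization, causal pathway diagramming and focus groups. The survey is not on the list.
- Protocol 9c describes sending the survey through REDCap and mentions no ID.
- Protocol 8a describes codes for dashboard cases. They isolate a clinic's data and are designed not to identify therapists. The SAP says that the dashboard route failed.
- The SAP names Qualtrics where the protocol names REDCap, and mentions no code.

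So no passage links the survey waves.

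**2. The plan's own power figure.** The plan states d = .36 to .48 at 80% power, for the superseded dashboard model. The parameters it refers to are not set out. As a check, assume 30 therapists with 5 cases each in both periods (n = 150 per period):

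d = (1.96 + 0.84) × √(2 × DE / 150), with DE = 1 + (5 − 1) × ICC

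- ICC .01: DE = 1.04, d = 0.33.
- ICC .30: DE = 2.20, d = 0.48.

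The upper end reproduces and the lower end does not. With 25 therapists the two ends are 0.36 and 0.53. The figure can be neither confirmed nor refuted, and this point does not depend on it. Only the 0.48 is borrowed below, as an illustrative shift.

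**3. What loss of linkage costs.** From the documents: 30 therapists (protocol 5a), three waves, alpha 0.05. Assumed: the same 30 people answer every wave, SD 1, a shift of 0.48 at both later waves, equal correlation ρ between waves, and no clinic effect. The documents give no ρ, so .3, .5 and .7 are shown.

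The wave means are 0, 0.48 and 0.48, with overall mean 0.32. The wave sum of squares is 30 × (0.32² + 0.16² + 0.16²) = 30 × 0.1536 = 4.608.

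*Linked:* the error variance is 1 − ρ, so the noncentrality is 4.608 / (1 − ρ) = 6.58, 9.22 and 15.36. The critical value of F(2, 58) is 3.16.

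*Rows paired arbitrarily:* the error mean square rises to about 1, while the wave means still vary as if correlated. The computed F is therefore about (1 − ρ) times the correct F, and the correct F must exceed 3.16 / (1 − ρ) = 4.51, 6.31 or 10.52 to reject.

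Simulation with 20,000 runs per cell:

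| ρ | Power, linked | Power, arbitrary pairing | Power, waves as independent groups | Type I error, linked | Type I error, arbitrary pairing |
|---|---|---|---|---|---|
| .3 | 0.606 | 0.412 | 0.421 | 0.051 | 0.016 |
| .5 | 0.763 | 0.376 | 0.384 | 0.053 | 0.003 |
| .7 | 0.936 | 0.325 | 0.334 | 0.050 | 0.0001 |

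The F approximation agrees: 0.60/0.76/0.94 linked and 0.41/0.37/0.31 with arbitrary pairing. A separate simulation with the Greenhouse-Geisser correction gave power one to two points lower when linked (59%/75%/93%) and similar values with arbitrary pairing (40%/36%/32%).

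**4. The clinic-level alternative.** A repeated-measures ANOVA on clinic means needs only a clinic label. The error df are 2 × (clinics − 1): 6 with four clinics (critical F 5.14) or 10 with six (critical F 4.10). The protocol gives both counts.

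**The case against.** The strongest reply is that anonymous does not mean unlinkable. A respondent can be unknown to the team and still carry a code, and section 9b shows that the team has used IDs without a crosswalk to match documents. The same section names REDCap as a storage place. The SAP never uses the word anonymous, and its reference to participants with partial data suggests that the analyst expects to see who lacks a wave. The form itself is not in the documents, so whether it has an ID field cannot be checked.

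This stands to the extent that a reader might infer the ANOVA is impossible, and the documents do not support that. A code may exist, and a version on clinic means would need no respondent link. But the SAP specifies neither, and participant-level LOCF would be undefined on clinic means.

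Three other stronger readings also fail:

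- A reader might take this for the trial's primary analysis. Protocol section 2c lists Aim 2 as secondary; the ANOVA is the SAP's only planned test.
- A reader might infer that mispairing would produce spurious significance. The working shows the opposite: under these assumptions the harm is lost power.
- A reader might suppose that staff turnover puts different people in each wave. The documents say nothing about turnover.

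The size of the loss also depends on ρ, which is assumed, and on a shift borrowed from a superseded model. At ρ = .3 the gap is clearly smaller.

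**Conclusion.** The concern holds in conditional form. The stated rules conflict: an anonymous survey with clinic-level inference on one side, a participant-level ANOVA with LOCF on the other, and no linking method in either document. If the collected responses carry a respondent-level code, the conflict is one of wording and is easily settled. If they do not, LOCF has no meaning and the participant-level ANOVA has no valid form. Arbitrary pairing would then cost between about 19 points of power (ρ = .3) and about 62 points (ρ = .7), with type I error between 1.6% and 0.01% instead of 5%. These sizes rest on 30 complete respondents, a 0.48 SD shift, equal correlation between waves and no clinic effect. The conflict itself rests on none of them.

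**What to change.** Confirm whether the responses already collected carry a respondent-level code.

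- **If they do:** describe the code in protocol sections 5a and 8a and in the SAP, and say that the survey is coded but not identifiable to the team. Use a self-generated code at any wave still to be collected. The cost is one field on the form and some wording; a few codes will not match.
- **If they do not:** drop LOCF and replace the repeated-measures ANOVA with a repeated cross-section analysis. This has a wave effect with clinic in the model, each wave uses only its own respondents, and the number of respondents per wave is reported. The SAP says that the form has already been sent, so this may be the branch that applies. It does not recover the power of linked data: treating waves as independent groups gave 0.42/0.38/0.33 above. The SAP should say so.

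Either way, state the unit of analysis in the SAP and reconcile it with the clinic-level aim in protocol section 5a. Reconcile the survey platform (REDCap or Qualtrics) in the same edit.
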